
Measures

Project measures captured information about implementation outcomes (both Facilitation and the implementation of MISSION-Vet), organizational readiness and VA health services utilization. Depending on the outcome, data were measured at the site, staff, and/or veteran level.

Implementation Outcomes

Consistent with recommendations for type III hybrid effectiveness-implementation designs, our primary outcome was MISSION-Vet uptake (as measured by number of MISSION-Vet sessions delivered) during the Implementation as Usual versus Facilitation time periods (Curran et al., 2012) and the secondary aim was to assess clinical outcomes (health service utilization). For this comparison of IU versus IF timeframes, we used a standardized facilitation tracking sheet completed by the external facilitators at the site level that included date, length of time, parties involved, activity type (Ritchie et al., 2019).

In addition, MISSION-Vet implementation was collected with a fidelity measure that was embedded in the Veterans' electronic medical record using a specially created service tracking note template to quantify the type and amount of MISSION-Vet delivered (Chinman et al., 2017). The MISSION-Vet Fidelity Measure tracks all the core elements of the MISSION-Vet treatment model, including Critical Time Intervention, DRT, Peer Support, vocational supports,

and trauma-informed care for each individual veteran. The fidelity index consists of 78 items assessing the presence or absence of certain activities within MISSION-Vet and will be captured in veterans' electronic medical records. Information captured in this note template included: which DRT sessions, peer support sessions, and Consumer Workbook exercises were completed; whether the MISSION-Vet Consumer workbook was provided; whether community activities were done with a Veteran (e.g., taken to appointment, NA/AA meetings, meetings with landlords); and referrals made to other services. Data on all veterans at all sites will be obtained from electronic medical records available in the VA's Corporate Data Warehouse.

Organizational Readiness

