An abbreviated version of the Organizational Readiness to Change Assessment (ORCA) context subscale and Jacobs' Implementation Climate survey, was used to examine organizational readiness resulting in a 21-item 5-point Likert scale to get at site and staff level readiness (Helfrich et al., 2009; Jacobs et al., 2014). Higher scores indicate greater organizational readiness and implementation climate. Following MISSION-Vet training, staff were asked to complete the organizational readiness survey and demographic survey regarding their age, sex, role/position, and tenure in VA.

Veteran Treatment Engagement

Treatment engagement as an outcome was captured with Veterans' medical records obtained from the VA Corporate Data Warehouse, which included number of MISSION-Vet contacts and other outpatient visits (mental health, substance use, medicine, primary care, emergency department, other, total). Each service utilization outcome was aggregated over the 1-year period following the date of Veterans' initial MISSION-Vet session.

Semi-structured Interviews

Semi-structured interviews were conducted for a formative and summative evaluation. The formative evaluation interviews elicited key stakeholders' experiences with, and perspectives on MISSION-Vet training, barriers to and facilitators of implementing MISSION-Vet

as well as to identify particular areas to target for Facilitation. Summative evaluation interviews identified stakeholder's experiences with Facilitation and needed adaptations to MISSION-Vet as well as veteran experiences with MISSION-Vet.

All semi-structured interviews were conducted by phone. Interview questions focused on evaluating the implementation of Facilitation, Implementation as Usual, and MISSION-Vet with particular focus on barriers to Facilitation, perceptions of strengths and weaknesses of MISSION-Vet for this population and setting, and leadership support for implementation in VA. The goal of the qualitative portion of this project was to get an understanding of what staff thought about MISSION-Vet itself and for researchers to understand the organizational context and then to identify barriers and facilitators to implementation of MISSION-Vet so that these areas can be addressed through Facilitation once it is activated.

Statistical Analysis Plan

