Our analytic strategy involved four components that align with the four study aims. Specifically, we examined: 1) pre-implementation organizational readiness; 2) IF process, including IF events; 3) MISSION-Vet implementation in the IU and IF time periods; and 4) association between MISSION-Vet and VA health services. Because the number of trained providers to deliver MISSION-Vet and the number of Veterans who received it at the seven homeless programs was too small for meaningful program comparison, our analysis focuses on a comparison between the two VAMCs (Sites A and B) rather than the seven individual programs when making comparisons for all measures of interest.

First, we examined organizational readiness using descriptive statistics and conducted comparisons of organizational readiness between the Sites A and B and by staff type (case manager vs. peer specialist), staff age, staff sex, and duration of employment with the VA using non-parametric Wilcoxon and Kruskal-Wallis tests. Second, we used descriptive statistics to examine IF events, including number, duration, and type of IF activities. Third, and similarly, we used descriptive statistics to examine implementation of MISSION-Vet. We summarize

information about the number and type of MISSION-Vet sessions provided overall, at the Veteran-level, and by VAMC. We also examined provision of MISSION-Vet separately by staff type (i.e., whether a case manager or peer specialist). Additionally, to assess the potential impact of IF on MISSION-Vet, we examined how the overall provision of MISSION-Vet changed over time both before and after the start of IF using descriptive measures of the number of MISSION-Vet sessions provided at each site by month. Our intent was to estimate the intervention effect using a statistical model in line with established practices for stepped wedge designs. However, because neither of the two sites provided any MISSION-Vet services in the IF period, there was no variation in the outcome of interest during this time thus rendering it impractical to estimate such a model. We therefore use descriptive statistics to examine the impact of IF on the provision of MISSION-Vet services.

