Fourth, we examined the relationship between receipt of MISSION-Vet and Veteran-level measures of engagement in clinical service (i.e., VA inpatient and outpatient services). To do so, we estimated a series of bivariate linear regression models in which our service utilization measures (i.e., number of outpatient and inpatient visits, by type, in the year after a Veteran's initial MISSION-Vet session) served as the outcomes of interest and the number of MISSION-Vet sessions in the year following a Veteran's initial MISSION-Vet session served as the predictor of interest in all models.

Qualitative Analysis

Each interview will be recorded and transcribed verbatim. A codebook will be developed with a priori codes based on Consolidated Framework for Implementation Research (Damschroder et al., 2009) along with emergent thematic coding (Boyatzis, 1998). For the formative evaluation, interviews will be coded and analyzed to synthesize data on organizational strengths and weaknesses and to identify key areas for the Facilitation strategy to target. The same process will be followed with the summative evaluation. The summative evaluation will

enable us to identify the differences and similarities experienced by participants both within LA sites and across the sites. These similarities and differences within and across sites will serve as a key “lessons learned” for subsequent efforts to facilitate use of MISSION-Vet across a larger number of sites in the VA.

Ajzen, I.F.M. (1977). Attitude-behavior relations: A theoretical analysis and review of empirical research. *Psychol Bull*, 84(5), 31

American Psychiatric Association. (2013). Diagnostic and statistical manual of mental disorders (DSM-5). Arlington, VA: American Psychiatric Publishing.

Boyatzis, R.E. (1998). Transforming qualitative information: Thematic analysis and code development. Thousand Oaks: Sage Publishing.

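### The Veteran-level models regress visit counts on MISSION-Vet sessions from the same 12 months with no covariates, so shared engagement alone can produce a slope; the plan needs a caveat and a prior-year adjusted companion model

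*Combined protocol and SAP*

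**What the plan says.** The fourth component of the Statistical Analysis Plan states that "we estimated a series of bivariate linear regression models in which our service utilization measures", namely inpatient and outpatient visits by type in the year after the first MISSION-Vet session, were the outcomes. The number of sessions in the year following the "initial MISSION-Vet session served as the predictor of interest in all models". Each model therefore has one outcome and one predictor. No prior use, site, severity or observation time is specified for these models.

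The Veteran Treatment Engagement section confirms the outcome window: "Each service utilization outcome was aggregated over the 1-year period following the date of Veterans' initial MISSION-Vet session". It also puts predictor and outcomes under one heading: "Treatment engagement as an outcome was captured with Veterans' medical records obtained from the VA Corporate Data Warehouse, which included number of MISSION-Vet contacts" together with the other outpatient visit types.

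The stated purpose varies. The Statistical Analysis Plan lists the target as "association between MISSION-Vet and VA health services" and later says "we examined the relationship between receipt of MISSION-Vet and Veteran-level measures of engagement in clinical service". The Implementation Outcomes section says "the secondary aim was to assess clinical outcomes (health service utilization", which gives the same data the status of a clinical outcome.

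**The concern.** Session counts were not randomised between Veterans. The Recruitment section makes willingness to take part a criterion, so the number of sessions plausibly tracks a Veteran's general readiness to attend. If the same trait drives other VA visits, the model regresses one engagement measure on another. Nothing in it separates a contribution of MISSION-Vet from what the Veteran would have used anyway. Identical windows also leave time order open, since a visit may come before most of the sessions.

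For services driven by need, such as emergency or inpatient care, the shared trait could work in the opposite direction and give a negative slope that looks like benefit.

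The predictor is also named loosely. The year opens at the first session, so every Veteran in the models had at least one. The slope compares more sessions with fewer among recipients; it says nothing about receipt versus non-receipt.

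At stake is how the secondary aim is read. The plan reports that the stepped-wedge effect model could not be fitted, so these are the only regression models left and readers may give them weight.

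**Working it through.** **What can be reproduced.** Nothing numerical: the documents give no Veteran count, session rate, visit rate, power or effect size for these models. The check below shows only that the bias is possible, its direction, and what adjustment does to it.

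**Assumed inputs, with no effect of MISSION-Vet.**
- Visits: Poisson, 2 per month × 12 months = 24, multiplied by exp(u + a).
- Sessions: 1 + Poisson, 4 per month × 6 months = 24, multiplied by exp(u + b).
- u is shared engagement, normal with log-SD s; a and b are each measure's own variation, log-SD 0.5.
- Prior-year visits follow the same law as visits. Everyone is followed for the full year.

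**Formulas.** With v = s² + 0.25:
- C = 24² · e^v · (e^(s²) − 1), the covariance of sessions and visits
- F = 24² · e^v · (e^v − 1)
- V = 24 · e^(v/2) + F, the variance of sessions, of visits and of prior-year visits
- Unadjusted slope = C / V
- Slope adjusted for prior-year visits = C(V − K) / (V² − C²), where K is the covariance of visits with prior-year visits. K = F if the whole visit propensity persists; K = C if only the shared part persists.

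**Result for s = 0.5 (v = 0.5).**
- C = 576 × 1.6487 × 0.2840 = 269.7
- F = 576 × 1.6487 × 0.6487 = 616.1
- V = 30.8 + 616.1 = 646.9, so V² − C² ≈ 345,700
- Unadjusted: 269.7 / 646.9 = 0.417 visits per session
- Adjusted, full persistence: 269.7 × 30.8 / 345,700 = 0.024, about 94% removed
- Adjusted, only the shared part persisting: 269.7 × 377.2 / 345,700 = 0.294, about 29% removed

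Simulation at n = 100 agrees. The median slope falls from 0.409 to 0.026 (94%) or from 0.414 to 0.288 (30%). With service months varying over 0–6 it falls from 0.433 to 0.025 (94%) or to 0.270 (38%).

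**Other values of s.** At s = 0, C = 0 and there is no spurious slope. At s = 0.25 the same formulas give 0.160, falling to 0.015 (91%) or 0.138 (14%).

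**A different model.** Take a gamma engagement factor with variance 0.10 to 0.50, sessions 1 + Poisson(5 × factor) and visits Poisson(20 × factor). The spurious slope is 1.3 to 2.9, falling to about 0.6–0.7 after prior-year adjustment. The size therefore depends on the inputs; the direction does not.

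**Would such a slope look like a finding?** In the first model the two variances are equal, so at s = 0.5 the correlation is also 0.417. The 5% threshold, r = t / √(n − 2 + t²), is 0.28 at an assumed n = 50 and 0.20 at n = 100.

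**Need-driven service.** At 0.1 visits per month (1.2 per year) with u acting in the opposite direction and s = 0.5, the slope is 24 × 1.2 × 1.6487 × (e^(−0.25) − 1) / 646.9 = −0.016.

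**Unequal time in care.** With s = 0 and 20% of Veterans assumed to leave care, the unadjusted slope is about 0.11 and adding prior-year visits leaves it there. The rejection rate rises from 20% to 32% at n = 100, because the covariate removes residual variance but not the shared exposure time.

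**Why slopes and not rejection rates.** At n = 50, s = 0.5, only the shared part persisting:

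| Model | Ordinary SE | HC3 SE |
|---|---|---|
| Sessions only | 82% | 58% |
| Plus prior-year visits and site | 51% | 29% |

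Reading from 82% to 29% mixes two changes. The switch of standard error alone accounts for 82 − 58 = 24 points, and it cannot remove confounding. The slope falls only from 0.41 to 0.28.

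**The case against.** The strongest reply is that the plan claims no more than the models deliver. It says association and relationship, and Study Design speaks of examining engagement among those receiving MISSION-Vet. An unadjusted slope is a legitimate estimate of an association. That stands, and it limits the point. A reader might infer that the plan makes a causal claim; the text does not. Only the Implementation Outcomes wording leans that way, and it specifies no effect estimate. Study Design's mention of outcomes literature describes existing work.

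The second reply is that the remedy is imperfect, which also stands. Prior-year visits are a noisy proxy for engagement, and with unequal follow-up the adjustment does not help and can raise the rejection rate. The near-complete correction needs full persistence, which makes the proxy almost perfect by construction.

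Third, a reader might infer that leaving out site is a defect, because the plan says "our analysis focuses on a comparison between the two VAMCs (Sites A and B) rather than the seven individual programs". That sentence explains why comparisons are made at VAMC level. It does not specify covariates for a slope among recipients, nothing in the documents shows site confounding, and the simulations gave site no effect.

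Fourth, the documents do not show that every Veteran was in VA care in the prior year, so a zero is ambiguous. This is correct and should be stated with the results.

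**Conclusion.** The point holds in a limited form. One predictor, identical windows and no covariates mean that shared engagement can produce a slope with no MISSION-Vet effect. With utilization presented as the secondary clinical outcome and no caveat, readers may take the slopes as outcomes of the intervention, which this model cannot support.

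The actual size is unknown. Across the assumed inputs with positive shared engagement, the spurious slope ran from 0.16 to 2.9 visits per session. None of these figures should be attached to this trial, and the documents do not support the inference that its slopes are in fact spurious or that its false-positive rate is known.

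Grade: cheap improvement, minor to moderate, confined to a secondary aim.

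**What to change.** 1. Keep the current unadjusted slopes. Beside them report models that add visits of the same type in the 12 months before the first session, from the Corporate Data Warehouse already in use. Label these post hoc, because the plan says the models were already estimated. Site may be added as a convenience covariate.
2. Use the same type of standard error in both models, so that any change reflects the covariate.
3. State that a prior-year zero may mean the Veteran was not in VA care.
4. As sensitivity analyses only, (a) add observed days and (b) use a landmark with sessions in months 1–6 and visits in months 7–12. Note that both condition on staying in care, which MISSION-Vet may itself affect, since its outreach sessions aim to engage clients.
5. Describe the predictor as number of sessions among Veterans with at least one session.
6. Add a sentence such as: *These are associations; adjustment does not remove confounding by engagement, and they are not read as effects of MISSION-Vet.*

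Cost: one more extract, a rerun and a few sentences. The downsides are one or two extra parameters in what may be a small sample, post hoc status, and probably smaller associations. If the extract proves impractical, items 5 and 6 still cost almost nothing.

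### Visit counts in aim 4 are fitted by linear regression with no count model or robust errors, so intervals can be misstated in either direction, most seriously too narrow where visits rise with skewed session counts

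*Combined protocol and SAP*

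**What the plan says.** The fourth component of the Statistical Analysis Plan gives the whole method for this aim. It states that "we estimated a series of bivariate linear regression models in which our service utilization measures" serve as outcomes, and defines these as the "number of outpatient and inpatient visits, by type, in the year after a Veteran's initial MISSION-Vet session". On the other side of the equation, "the number of MISSION-Vet sessions in the year following a Veteran's initial MISSION-Vet session served as the predictor of interest in all models". The Veteran Treatment Engagement section under Measures fixes the window: "Each service utilization outcome was aggregated over the 1-year period following the date of Veterans' initial MISSION-Vet session". That section lists outpatient visits by type, including emergency department and total; the SAP adds inpatient visits.

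For these models the documents name no count distribution, transformation, robust or bootstrap standard error, or residual check. For the organizational readiness scores, by contrast, the SAP moves away from normal-theory methods, "using non-parametric Wilcoxon and Kruskal-Wallis tests".

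The documents also do not say which standard error was used. For aim 4 they give no number of Veterans, slope, interval, p-value or significance level, and they do not describe the distribution of visits or sessions. The Implementation Outcomes section makes health service utilization the secondary aim.

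**The concern.** Visit counts usually have a variance that grows with their mean. Ordinary least squares assumes one residual variance at every session count. Suppose visits rise with sessions and a few Veterans have many sessions. Those Veterans then have both the most leverage on the slope and the noisiest outcomes, and the default standard error averages this away. This problem is separate from confounding and clustering: it would arise even if Veterans were independent and comparable. A larger sample does not remove it.

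Two features of the trial make it worth attention. The stepped-wedge model for uptake was given up, so these regressions are the only fitted models left. MISSION-Vet also aims to engage Veterans in care and link them to services, so a positive slope is plausible for several outcomes, and that is the direction in which default intervals would be too narrow.

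**Working it through.** **1. Figures to reproduce.** There are none. The documents state no sample size, slope or standard error for aim 4, so every numerical input below is an assumption.

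**2. Formula.** For Veteran i with sessions x_i and visit variance v_i, the least-squares slope b has

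- true variance: Σ(x_i − x̄)² v_i / [Σ(x_i − x̄)²]²
- default estimate: (average v) / Σ(x_i − x̄)², approximately.

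The two agree when the leverage-weighted average of v equals its plain average. For negative binomial visits with mean μ and dispersion k, v = μ + μ²/k.

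**3. Why shape matters.** Take mean visits 15, k = 1, and an elasticity of 0.3 at the average session count.

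- *Right-skewed sessions, mean 5.* Slope = 0.3 × 15/5 = 0.90 visits per session. At 1 session, μ = 15 − 0.9 × 4 = 11.4 and v = 11.4 + 11.4² = 141. At 24 sessions (the 13 DRT plus 11 peer-led sessions in the MISSION-Vet Intervention section), μ = 15 + 0.9 × 19 = 32.1 and v = 32.1 + 32.1² = 1,063. The point with far more leverage has 1,063/141 = 7.5 times the variance.
- *Sessions spread evenly over 1-24, mean 12.5.* Slope = 0.3 × 15/12.5 = 0.36. The two ends have equal leverage, with v = 129 (μ = 10.86) and v = 385 (μ = 19.14). Their average is 257, against 15 + 15² = 240 at the centre. High and low variance nearly cancel.

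**4. Simulation by elasticity.** Visits were negative binomial with mean 15 and k = 0.5 or 1; n was 30, 60, 100 or 200; there were 4,000 replicates per setting. Coverage is of nominal 95% intervals around the mean estimated slope. The rows below are for n = 100, k = 1. The last column is a check, 2Φ(1.96 × ratio) − 1.

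| Sessions | Elasticity | True SD | Default SE | Ratio | Coverage | Check |
|---|---|---|---|---|---|---|
| Skewed | −0.3 | 0.254 | 0.348 | 1.37 | 99.1% | 99.3% |
| Skewed | 0 | 0.330 | 0.332 | 1.01 | 95.5% | 95% |
| Skewed | 0.1 | 0.395 | 0.333 | 0.84 | 90.2% | 90% |
| Skewed | 0.3 | 0.537 | 0.340 | 0.63 | 78.8% | 78% |
| Skewed | 0.6 | 0.766 | 0.367 | 0.48 | 65.9% | 65% |
| Even | 0.3 | 0.227 | 0.228 | 1.00 | 95.2% | 95% |

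Over all n and k with skewed sessions, coverage was 95-96% at no association, 90-92% at 0.1, 77-82% at 0.3 and 62-70% at 0.6. It was 97-99% for negative slopes. With evenly spread sessions it was 92-96% throughout.

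**5. Simulation by percentage change per session.** Sessions were 1 plus a negative binomial (mean 7, dispersion 0.7). Baseline visits were 20 (dispersion 1) or 1 (dispersion 0.5), n was 50 to 200, and the mean was log-linear in sessions. Coverage with skewed sessions was:

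- +1% per session: 90-92%
- +3%: 68-80%
- +5%: 43-54%
- none: 95-96%
- −3%: 98-99%

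With evenly spread sessions it was 91-96%. The +5% figure is the least stable, because it depends on how the far tail of session counts is handled.

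**6. Do robust errors suffice?** With HC3 errors and the skewed inputs of step 4, coverage was 90-92%, 85-90% and 81-89% at elasticities 0.1, 0.3 and 0.6. That is better for clear positive slopes but still short of 95%.

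**The case against.** The strongest reply has four parts.

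- **Direction.** A reader might infer that default errors are far too narrow whenever visits vary with sessions, and so that every aim 4 slope has the wrong precision. The documents do not support that. With skewed sessions and a negative slope, which is conceivable for emergency or inpatient use, the errors are too wide. With evenly spread sessions or no association they are about right. This part stands in full.
- **Nothing is reported.** The documents contain no aim 4 interval and do not say that constant-variance errors were used, so no published precision can be called wrong. This also stands. Constant variance is only the ordinary reading of linear regression without further detail.
- **Sample size.** The SAP says "the number of Veterans who received it at the seven homeless programs was too small for meaningful program comparison". That concerns comparison between programs. It does not establish that the Veteran-level regressions had a small sample. Likewise, skewed sessions, mostly zero outcomes and dominance by one or two heavy users are plausible but not documented.
- **The remedy has its own variance assumption.** Negative binomial intervals covered 93-96.5% when the data came from that model, but about 90-92% under lognormal-Poisson heterogeneity. In one check (n = 100, +3% per session, 300 replicates) they covered only 70% when dispersion grew with sessions. They held at 96-98% with a linear mean or zero inflation. This argues for a check on the variance assumption. It does not argue for leaving the linear model with no check at all.

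**Conclusion.** The gap is real but narrower than it may first look. The SAP applies linear regression to visit counts and specifies nothing that protects the intervals against unequal variance. Under the ordinary reading, their validity depends on two things that a reader cannot see: the sign of each slope and the shape of the session distribution.

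The serious case is a positive slope with right-skewed sessions. There the loss runs from a few points of coverage for a weak association to coverage of about half for a strong one. In the opposite case the intervals are conservative. A test of no association is not made anti-conservative by this mechanism.

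All sizes rest on assumed sample sizes, distributions and slopes. The aim is secondary and associational, and the descriptive primary comparison of uptake is untouched. Severity is SHOULD-FIX, with moderate confidence.

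**What to change.** In the fourth component of the Statistical Analysis Plan, replace the linear models with wording such as: *Each one-year visit count will be analysed by negative binomial regression with a log link, with the number of MISSION-Vet sessions as predictor, and reported as a rate ratio with its 95% confidence interval. Bootstrap intervals will be given as a check on the variance assumption. Each estimate will be shown with and without the Veterans with the highest session counts.* The cut-off for the highest counts should be fixed in the text.

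If an additive effect is wanted, report the average marginal difference in visits with a bootstrap interval. Keeping linear regression and adding robust errors would be only a partial repair, as step 6 shows. The bootstrap was not simulated here, so it serves as a check and is not a guarantee of coverage.

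The cost is a short change of wording and a rerun on data already extracted. Effects become rate ratios instead of visits per session, and intervals will usually widen. Because the plan describes this analysis in the past tense, the rerun should be labelled as a change made after the linear models were fitted.

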intense treatment is needed. They are also trained to provide ongoing support for Veterans who are receiving treatment from a specialized PTSD program or to serve Veterans who do not require specialized PTSD services. MISSION-Vet was offered for approximately 2-hours a week for 6-months, and service delivery was guided by a Treatment Manual (Smelson et al., 2011a). Veterans could also receive a MISSION-Vet Workbook that includes assignments reinforcing recovery (Smelson et al., 2011b).

Participation Sites

Site Composition

This project was conducted at two VA Medical Centers (VAMCs; hereafter Sites A and B) and offered to staff at seven homeless programs (four locations at Site A and three locations at Site B) with the unit of measurement being the two VAMCs. The two VAMCs were selected because of the size and scope of the healthcare systems, geographic dispersion, and the rate of homelessness in the regions (Department of Veterans Affairs, 2014). Site A was in a large VA urban setting, serving approximately 83,000 unique Veterans annually with the highest-level complexity, and two on-site residential buildings, and two off-site buildings. Site B was a smaller suburban medium complexity VA serving approximately 18,000 unique Veterans annually, with one on-site and off-site residential building. Both Sites A and B had community-based non-residential treatment which included housing placement, case management, linkages to mental health and substance use programming, but not MISSION-Vet.

Recruitment

There were two groups of participants in the study: staff and clients. The first group were the case managers and peer specialists delivering MISSION-Vet; staff participation was voluntary with no incentives provided. The second group were, Veterans (clients) being served by these staff in their respective VA homeless programs. Staff were encouraged to follow the recommended MISSION-Vet inclusion and exclusion criteria. This included: (1) enrolled in a VA homeless program at one of the implementation sites; (2) met Diagnostic and Statistical Manual of

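### The Veteran-level utilization regressions have no site term and no described method for dependence, so the pooled slope is open to site confounding and ordinary standard errors may be too small

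*Combined protocol and SAP*

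**What the plan says.** The fourth component of the Statistical Analysis Plan concerns "Veteran-level measures of engagement in clinical service". For these, "we estimated a series of bivariate linear regression models in which our service utilization measures" are the outcomes, counted over the year after the first MISSION-Vet session. The number of sessions in that same year "served as the predictor of interest in all models". A bivariate model has one regressor, so site, program and staff are not in it. No random effect, robust variance or clustered variance is mentioned.

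The data are nested. Under Recruitment, the clients are those "being served by these staff in their respective VA homeless programs". Under Site Composition there are "seven homeless programs (four locations at Site A and three locations at Site B"), and the two VAMCs differ: Site A is described as "serving approximately 83,000 unique Veterans annually with the highest-level complexity" in an urban setting, while Site B is suburban, of medium complexity, and serves about 18,000 Veterans a year.

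The SAP also says that comparisons are made between the two VAMCs and not among the seven programs, because staff and Veteran numbers were too small. That rule governs comparisons. It does not put site into the utilization regressions.

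**The concern.** There are two separate problems.

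- **The slope.** If one VAMC delivered more sessions per Veteran and its Veterans also made more visits for unrelated reasons, a pooled slope would show an association between sessions and visits even where none exists within either site.
- **The standard error.** Sessions are delivered by staff, and visits depend partly on what a program and its VAMC offer. If both are correlated among Veterans who share staff or a program, the ordinary standard error understates the sampling variation of the slope.

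The planned stepped-wedge model was not fitted, so these are the only regression models left in the plan. Their results are meant to add to the evidence on MISSION-Vet outcomes. A positive slope that reflects site, or an interval that is too narrow, could be read as support that the data do not give.

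**Working it through.** **Inputs.** From the documents: one regressor, the Veteran as unit of analysis, seven programs (four and three), two VAMCs. The documents give no number of Veterans or staff, caseload, intraclass correlation, significance level, slope or standard error for this component. There is thus no stated figure to reproduce, and every numerical input below is assumed.

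**1. Standard error.** For equal clusters of m Veterans, with intraclass correlations rho_x for sessions and rho_y for visits, the variance of the slope is inflated relative to the ordinary formula by

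VIF = 1 + (m − 1) × rho_x × rho_y,

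and the ordinary standard error is too small by the factor √VIF. The approximate two-sided type I error at nominal 5% is 2 × [1 − Φ(1.96/√VIF)]. For example, m = 10, rho_x = 0.4 and rho_y = 0.1 give 1 + 9 × 0.04 = 1.36, √1.36 = 1.17, and a type I error of 9.3%. The last column below is from 4,000 simulated data sets per row, with 10 staff and a true slope of zero.

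| m | rho_x | rho_y | VIF | √VIF | Type I, formula | Type I, simulated |
|---|---|---|---|---|---|---|
| 5 | 0.2 | 0.05 | 1.04 | 1.02 | 5.5% | 5.7% |
| 5 | 0.4 | 0.1 | 1.16 | 1.08 | 6.9% | 6.5% |
| 5 | 0.5 | 0.2 | 1.40 | 1.18 | 9.8% | 9.2% |
| 10 | 0.2 | 0.05 | 1.09 | 1.04 | 6.0% | 5.9% |
| 10 | 0.4 | 0.1 | 1.36 | 1.17 | 9.3% | 8.6% |
| 10 | 0.5 | 0.2 | 1.90 | 1.38 | 15.5% | 14.5% |

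If rho_x = 0 or rho_y = 0, VIF = 1 and there is no understatement.

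**2. Site confounding.** Let the within-site slope be zero, let a share p of Veterans be at one site, and let the sites differ by dx in sessions and dy in visits, both in within-site standard deviations. The pooled slope is then

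p(1 − p) × dx × dy / [1 + p(1 − p) × dx²].

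- p = 0.5, dx = dy = 0.5: 0.25 × 0.25 / (1 + 0.25 × 0.25) = 0.0625/1.0625 = 0.059.
- p = 0.5, dx = dy = 1: 0.25/1.25 = 0.20.
- p = 0.8, dx = dy = 0.5: 0.04/1.04 = 0.038.
- p = 0.8, dx = dy = 1: 0.16/1.16 = 0.138.
- dx = 0 or dy = 0: zero.

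**3. Both together.** With seven equal programs (four and three), rho_x = 0.3, rho_y = 0.1 and site differences of 0.5 SD on both variables, simulated rejection under a zero slope was 12.1% with 70 Veterans and 19.3% with 140. Program fixed effects, which also absorb site, brought this to 5.2% and 4.8%.

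**4. How the remedy behaves.** These are further simulations with a fixed site term plus CR2 errors and Satterthwaite degrees of freedom.

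- Ten staff with 10 Veterans each: rejection was 4.7%, 4.1% and 5.0% for the three pairs of correlations in the table.
- Seven equal programs of 20 Veterans with the site differences in step 3: the bivariate model rejected 20.1%, a site term alone 9.7%, and both parts together 4.5%.
- Seven unequal programs (assumed sizes 20, 10, 5, 3, 7, 3, 2; 50 Veterans): median degrees of freedom were about 3.2, intervals were about 44% wider than ordinary intervals with the same site term, and rejection was 3.4% to 3.8%, which is conservative.

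**The case against.** The strongest reply is that the documents establish the structure but not the harm. A reader might infer that the standard errors are wrong in every one of these models. That does not follow. Understatement needs both sessions and visits to cluster, and no correlation is reported for either. Session counts also depend on each Veteran's willingness and engagement, not only on staff. The SAP does not say how standard errors were computed; ordinary ones are the natural reading, but no interval or p-value is shown.

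A reader might also infer from the site descriptions that site confounding is present. The figures of 83,000 and 18,000 are whole-facility volumes. They do not show that sessions or visits per homeless-program Veteran differ, and both sites are said to offer the same kind of community-based care. Confounding needs a difference on both variables.

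Two practical objections also stand. The described content of the note template does not list staff identity, although the planned analysis by staff type suggests that some provider information exists. And a Veteran may be served by both a case manager and a peer specialist, so nesting in a single staff member is a simplification. Clustering on seven small, unequal programs is possible but weak.

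Two replies do not stand. Two sites are too few for a random site effect or site-level clustering, but not for a fixed indicator. And programs too small to compare are still programs whose Veterans may be correlated.

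**Conclusion.** The concern holds in a conditional form. The models leave out site and describe no handling of dependence, so the slope mixes within-site and between-site association, and ordinary standard errors are likely too small if sessions and visits both cluster by staff or program.

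The size cannot be determined from the documents. Under the assumed 10 staff with 5 to 10 Veterans each, type I error runs from about 6% to 14%. It could be nominal if either variable does not cluster, and higher with larger clusters or with site differences on both variables. These error rates matter only to the extent that the slopes are tested or given intervals.

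This is a cheap improvement to a secondary, associational analysis, not a demonstrated error. The primary uptake comparison is untouched. Adjusting for site does not remove confounding at the Veteran level, so the slope would still not be a treatment effect.

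**What to change.** In the fourth component of the Statistical Analysis Plan, add a fixed indicator for Site A versus Site B to every utilization model and report the site-adjusted slope. Site is known for every Veteran. Since the text describes these models as already estimated, this means re-running them.

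As a sensitivity analysis, report CR2 standard errors with Satterthwaite degrees of freedom, clustered on the treating staff member or team if the records allow that link, and otherwise on program. If program is used, state that seven unequal programs give few effective degrees of freedom and conservative intervals. Also state the number of Veterans, staff and programs, and that the results are associations open to Veteran-level confounding.

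The cost is a few lines of code and SAP wording, one degree of freedom for site, and wider intervals in the sensitivity analysis, considerably wider if only program can be used.
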